### 3.2 Rationale for Study Design

The study is placebo-controlled in order to compare the current standard of care of no chelation vs. early-start chelation, on both safety and efficacy measures.

Apart from the use of placebo, the design is similar to that of the earlier investigator-led open-label study, in which the control group received no treatment. The same parameters

that were used in that study to measure iron overload—serum ferritin, transferrin saturation, and labile plasma iron—are used here, with the difference of applying a criterion of 60% rather than 70% for transferrin saturation. The same criterion of discontinuing patients from the study when they reach a serum ferritin level  $\geq 1000 \mu\text{g/L}$  at 2 consecutive visits is maintained, which ensures that patients who are ready to begin standard chelation therapy will not be delayed in doing so.

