### **Early termination visit (if applicable)**

From Month 2 to Month 11, a patient who is determined to have had a serum ferritin level  $\geq 1000 \mu\text{g/L}$  at 2 consecutive visits will be terminated from the study, and is to return for an early termination visit as soon as possible. The following procedures will be done:

- Collect blood samples for hematology and blood chemistry assessments
- Collect a urine specimen for urinalysis
- Perform a physical examination (to be completed by the investigator or a qualified delegate)
- Measure vital signs (heart rate, blood pressure, and body temperature)
- Measure weight and height/length
- Review and update transfusion history
- Ask about any adverse events that have occurred and concomitant medications that have been taken since the last site visit
- Additionally review the diary card for information on adverse events and use of concomitant medications, and file the diary card with the source documents
- Collect study medication containers, and check them to calculate treatment compliance

For patients who withdraw early for reasons other than reaching the serum ferritin threshold, the early termination visit will include all procedures done at the Month 12 visit except for measurement of prolactin.

Participation in the study is now complete. Patients whose SF level is still below  $1000 \mu\text{g/L}$  at 12 months will be offered participation in an extension study, LA55-EXT, in which they will continue to receive their assigned study product for up to 2 more years. Patients who are terminated early because they have already reached the  $1000 \mu\text{g/L}$  threshold will not be eligible to enroll in the extension study.

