## 3. Study Design

### 3.1 Description of Study Design

This is a multi-center, randomized, double-blind, placebo-controlled study in infants and young children newly diagnosed with transfusion-dependent  $\beta$ -thalassemia. Patients start on a red blood cell (RBC) transfusion regimen designed to maintain a hemoglobin level  $> 9$  g/dL, but still have a serum ferritin level well below the threshold that current treatment guidelines state should be reached before iron chelation therapy can begin.

Screening is conducted within 14 days prior to the start of dosing. At baseline, eligible participants are randomized in a 1:1 ratio to receive either deferiprone oral solution 80 mg/mL or matching placebo. Visits are scheduled approximately monthly (every  $30 \pm 10$  days) for the determination of levels of serum ferritin (SF), labile plasma iron (LPI), and transferrin saturation (TSAT), and for assessments of safety that include determination of liver enzymes (ALT and AST) and growth measurements.

Dosage begins at 25 mg/kg/day, divided into 3 doses (t.i.d.), and is increased to 50 mg/kg/day (divided t.i.d.) after 2 weeks. After that, it is increased to 75 mg/kg/day (divided t.i.d.) for patients who meet either of the following criteria:

- An SF value  $\geq 800 \mu\text{g/L}$  (but still below  $1000 \mu\text{g/L}$ ) and/or an LPI value  $\geq 0.6 \mu\text{M}$  and/or a TSAT value  $\geq 60\%$  at 2 consecutive visits, or
- An increasing trend in any of the above 3 measures (SF, LPI, and/or TSAT) at 3 consecutive visits, regardless of value

If a single occurrence of any of the following is detected at any time, treatment is interrupted:

- SF value below the lower reference range for the child's age
- Mild neutropenia, defined as an absolute neutrophil count (ANC)  $< 1.5 \times 10^9/\text{L}$  but  $\geq 1.0 \times 10^9/\text{L}$
- Fever or other signs of infection, prior to confirmation that ANC is  $\geq 1.5 \times 10^9/\text{L}$

As these parameters are known to fluctuate, the assessment is repeated as soon as possible to verify that treatment interruption is necessary. Treatment is re-initiated after the abnormally low SF or ANC level is recovered, or when the fever or infection resolves or is determined to not be indicative of neutropenia.

If moderate neutropenia (ANC  $< 1.0 \times 10^9/\text{L}$ ) is confirmed, the patient is withdrawn from the study.

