Patients remain in the study for 12 months or until their SF level is found to be  $\geq 1000 \mu\text{g/L}$  at 2 consecutive visits, whichever comes first. Since SF level may be impacted by the presence of infection, it must additionally be verified that the child has had no signs of infection in the previous 7 days, including the day of the visit, and that the level of C-reactive protein (CRP) is no greater than 20% higher than the normal range for the patient's age. If there are signs of infection and/or the CRP level is above this threshold, the SF level must be checked again a minimum of one week later. (Note: If an investigator has valid reason to believe that an SF level  $\geq 1000 \mu\text{g/L}$  may be attributable to infection even if this is not indicated by the CRP result, SF may be rechecked once more a minimum of one week later.)

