#### 4.1.1 Serum Ferritin ( $\mu\text{g/L}$ )

Ferritin is a protein that stores iron in a non-toxic form, transports it to areas where it is required, and releases it in a controlled manner, thereby acting as a buffer against iron deficiency and iron overload. It is mainly found in tissues, but small amounts are measured in the serum, where it can serve as an indirect but easily measurable marker of the total amount of iron stored in the body. (Drawbacks of using it as a marker include lack of specificity, as disorders other than iron overload can cause large amounts of ferritin to be released into the circulation, and inter-patient variability.) Levels of serum ferritin above 1000 ng/mL are often considered to be associated with iron toxicity. In young children who have only recently begun an RBC transfusion regimen, it takes some time for this level to be reached, but in the absence of chelation it inevitably is reached.

Serum ferritin is measured at each visit, and the time to reach a level  $\geq 1000 \mu\text{g/L}$  will be compared between the treatment arms. Patient is to be withdrawn from the study when they attain a serum ferritin level  $\geq 1000 \mu\text{g/L}$  at 2 consecutive visits provided that the child has had no signs of infection in the previous 7 days and that CRP level is not greater than 20% higher than the normal range for the patient's age.

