## 5.6 Analysis of Efficacy

The percentage of patients who have not reached levels of  $LPI \geq 0.6 \mu M$ ,  $TSAT \geq 60\%$ , or  $SF \geq 1000 \mu g/L$  will be compared between the two treatment groups at each monthly time point as well as at the end of study, using the Fisher's exact test. (Note: the repeated SF value will be used to determine this for those patients whose SF is  $\geq 1000 \mu g/L$ .)

The effect of baseline value on each of the 3 efficacy endpoints will be examined in a covariate analysis. As an example for serum ferritin, the following SAS code of MIXED procedure will be used to produce the differences in Least Squares (LS) Mean of change in serum ferritin at Months 1, 2, 3, 4, 5, 6, 7, 8, 9, 10, 11, and 12 between deferiprone and placebo groups and the corresponding 95% confidence intervals.

```

proc mixed data=sf;
  class patient base_sf treat month;
  model sf_change = base_sf treat month treat*month /
    noint solution ddfm=kr;
  repeated month / Patient=patient(treat) type=ar(1);
  lsmeans treat*month;
  estimate 'Deferiprone - Placebo at Month 1'
    treat 1 -1
    treat*month  1 0 0 0 0 0 0 0 0 0 0 0
                 -1 0 0 0 0 0 0 0 0 0 0 0 / cl alpha=0.05;
  estimate 'Deferiprone - Placebo at Month 2'
    treat 1 -1
    treat*month  0 1 0 0 0 0 0 0 0 0 0 0
                 0 -1 0 0 0 0 0 0 0 0 0 0 / cl alpha=0.05;
  estimate 'Deferiprone - Placebo at Month 3'
    treat 1 -1
    treat*month  0 0 1 0 0 0 0 0 0 0 0 0
                 0 0 -1 0 0 0 0 0 0 0 0 0 / cl alpha=0.05;
  estimate 'Deferiprone - Placebo at Month 4'
    treat 1 -1
    treat*month  0 0 0 1 0 0 0 0 0 0 0 0
                 0 0 0 -1 0 0 0 0 0 0 0 0 / cl alpha=0.05;
  estimate 'Deferiprone - Placebo at Month 5'
    treat 1 -1
    treat*month  0 0 0 0 1 0 0 0 0 0 0 0
                 0 0 0 0 -1 0 0 0 0 0 0 0 / cl alpha=0.05;
  estimate 'Deferiprone - Placebo at Month 6'
    treat 1 -1
    treat*month  0 0 0 0 0 1 0 0 0 0 0 0
                 0 0 0 0 0 -1 0 0 0 0 0 0 / cl alpha=0.05;

```

```

estimate 'Deferiprone - Placebo at Month 7'
  treat 1 -1
  treat*month  0 0 0 0 0 0  1 0 0 0 0 0
                0 0 0 0 0 0 -1 0 0 0 0 0/ cl alpha=0.05;
estimate 'Deferiprone - Placebo at Month 8'
  treat 1 -1
  treat*month  0 0 0 0 0 0  1 0 0 0 0
                0 0 0 0 0 0 0 -1 0 0 0 0/ cl alpha=0.05;
estimate 'Deferiprone - Placebo at Month 9'
  treat 1 -1
  treat*month  0 0 0 0 0 0 0 0  1 0 0 0
                0 0 0 0 0 0 0 0 -1 0 0 0/ cl alpha=0.05;

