estimate 'Deferiprone - Placebo at Month 10'
  treat 1 -1
  treat*month  0 0 0 0 0 0 0 0 0  1 0 0
                0 0 0 0 0 0 0 0 0 -1 0 0/ cl alpha=0.05;
estimate 'Deferiprone - Placebo at Month 11'
  treat 1 -1
  treat*month  0 0 0 0 0 0 0 0 0  1 0
                0 0 0 0 0 0 0 0 0 0 -1 0/ cl alpha=0.05;
estimate 'Deferiprone - Placebo at Month 12'
  treat 1 -1
  treat*month  0 0 0 0 0 0 0 0 0  1
                0 0 0 0 0 0 0 0 0 0 -1/ cl alpha=0.05;
run;

```

A Kaplan-Meier survival curve for the time to reach a serum ferritin level  $\geq 1000 \mu\text{g/L}$ , an LPI value  $\geq 0.6 \mu\text{M}$ , or a TSAT value  $\geq 60\%$  will be generated for the two treatment groups. Log-rank test will be used for comparing the two survival curves for each of the 3 efficacy endpoints.

As an example, for serum ferritin, the following SAS code of LIFETEST procedure will be used to compare the two survival curves. A variable status is the censoring indicator. A status of 1 indicates an event time when a serum ferritin level reaches  $\geq 1000 \mu\text{g/L}$  and a status of 0 indicates the event of serum ferritin level  $\geq 1000 \mu\text{g/L}$  has not occurred by the end of the study.

```

proc lifetest data=sf method=km plot=(s) graphics;
  time month*status(0);
  strata treat;
run;

```

Trend analysis over time for LPI, TSAT, and SF measures will be performed to compare the rate of change per month in these measures between the two treatment groups. As an example, for serum ferritin, the following SAS code of MIXED procedure will be used to compare the two slopes between the two treatment groups:

```
proc mixed data=sf;
  class treat patient;
  model sf = treat month treat*month / noint solution;
  repeated / type=ar(1) Patient=patient(treat);
  estimate 'Slope for deferiprone' month 1 treat*month 1 0;
  estimate 'Slope for placebo' month 1 treat*month 0 1;
  estimate 'Slope for deferiprone minus placebo' treat*month 1 -1;
run;
```

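### SAP 5.6 LS-mean model: baseline ferritin is coded as a class factor, and the AR(1) covariance under ferritin-triggered withdrawal can bias the Month-12 difference and make its interval too narrow

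*SAP*

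**What the plan says.** SAP 5.6 gives two PROC MIXED blocks for serum ferritin, as the example for all three iron measures.

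- **LS-mean model** (change from baseline by month; Table 14.2.1.3). The CLASS line is "class patient base_sf treat month" and the covariance line is "repeated month / Patient=patient(treat) type=ar(1"). There is no RANDOM statement.
- **Trend model** (slope per month; Table 14.2.1.4). The covariance line is "repeated / type=ar(1) Patient=patient(treat").

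Ferritin itself decides who is still observed. SAP 3.1: "Patients remain in the study for 12 months or until their SF level is found to be" at or above 1000 µg/L at two consecutive visits. SAP 4.1.1 repeats it: "Patient is to be withdrawn from the study when they attain a serum ferritin level" of that size, subject to the infection and CRP check. Protocol 3.2 gives the reason, "which ensures that patients who are ready to begin standard chelation therapy will not be delayed in doing so".

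For these children the early termination visit in Protocol 5.1 lists "Collect blood samples for hematology and blood chemistry assessments" and no ferritin. The End of Study column of the schedule (Protocol Table 5.1, SAP Table 1) marks ferritin, and its footnote 2 covers threshold terminations.

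No other covariance, robust standard error or missing-data sensitivity analysis is named for these models. The only sensitivity analysis in the SAP is an optional COVID-19 exclusion.

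**The concern.** In PROC MIXED a CLASS variable is a factor. With `base_sf` there, the model fits a separate mean for each distinct baseline ferritin. A level that occurs in one arm only says nothing about the difference between arms, so the covariate adjustment removes the comparison it was meant to sharpen. `Patient=` is also not an option of the REPEATED statement; it has to be read as `SUBJECT=`.

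The covariance matters because of the withdrawal rule. Later ferritin is missing because earlier observed ferritin was high. A likelihood model can handle that, but only if its covariance describes how a child's early values predict the later ones. AR(1) lets that information fade with lag. If some children rise persistently faster, the model treats those who left as drifting back toward the arm mean. More placebo children leave, so the error does not cancel between arms in general.

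At stake are the Month-12 ferritin effect size and its interval in Table 14.2.1.3.

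**Working it through.** **The plan's own figure.** Protocol 9.2 claims over 90% power for 70% against 20% with 32 per arm. Normal approximation: z = (0.5·√32 − 1.96·√(2·0.45·0.55)) / √(0.21 + 0.16) = (2.828 − 1.379) / 0.608 = 2.38, power 0.991. The exact Fisher power is 0.983. The claim is met, and 70%/20% is used below to set the arm means. The documents give no figure for the mixed models.

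**Baseline in CLASS.** Assume whole-number baselines spread evenly over the eligible range (above 200 to 600, about 400 values). Expected cross-arm tied pairs = 32 × 32 / 400 = 2.56. The whole between-arm comparison would rest on about that many pairs. In simulated trials (below), 1.9 to 2.2 levels were shared on average, and no level was shared in 10–15% of trials at noise SD 80. At equal slope SD 20 the printed contrast was not estimable in 15% of trials. Otherwise its mean SE was 71 against a true sampling SD of 156, with 57% coverage.

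**Why AR(1) does not fit differing slopes.** Let slope SD be τ and visit noise SD σ. The change from baseline at month m has variance m²τ² + 2σ², and months j and k have covariance jkτ² + σ². With τ = 20 and σ = 80:

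- Variance at Month 1: 400 + 12,800 = 13,200. At Month 12: 57,600 + 12,800 = 70,400, which is 5.3 times as large.
- Correlation of Months 1 and 2: 7,200 / √(13,200 × 14,400) = 0.52. Of Months 11 and 12: 59,200 / √(61,200 × 70,400) = 0.90.

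AR(1) allows one variance and one adjacent-month correlation.

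**Size.** Inputs from the documents: 32 per arm, baseline 200–600, withdrawal after two consecutive values of 1000 or more, 70%/20% below 1000 at Month 12. Assumed: slope SD, noise SD (80 unless stated), straight-line rise, no other dropout, baseline entered as continuous. Bias is the mean estimate minus the true difference without withdrawal. For slope SD 20, true = 12 × (37.6 − 69.3) = −380 µg/L.

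Simulation A: baseline normal (400, SD 100) truncated to 200–600, Kenward–Roger, 180–300 trials per cell. Simulation B: uniform baseline, 60 df, 600 trials per cell.

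| Slope SD placebo / deferiprone | Sim. | AR(1) Month-12 error | 95% CI coverage |
|---|---|---|---|
| 0 / 0 | A | 6.7% understated | 92% |
| 2 / 2 | B | 18/212 = 8% understated | 92.5% |
| 10 / 10 | A | 17.4% understated | 77% |
| 15 / 15 | A | 24.5% understated | 62% |
| 20 / 20 | B | 98/380 = 26% understated | 54% |
| 25 / 25 | A | 29.4% understated | 47% |
| 30 / 30 | B | 157/521 = 30% understated | 41% |
| 30 / 15 | A; B | 56%; 236/443 = 53% understated | 3%; 3.5% |
| 15 / 30 | A; B | none; 6/392 = 2% understated | 86%; 91% |
| 10 / 35 | B | 48/386 = 12% overstated | 82% |

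With noise 50 and 100 (A, slope SD 15–25) the understatement was 20–23% and 26–34%. Without withdrawal the bias disappears but the interval is still too narrow: 85% coverage at slope SD 20 (SE 46 against a sampling SD of 64).

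**`type=un` on the same data (A).** At equal slope SD 0–35, Month-12 bias was within 1.3% and coverage 94–95%. At 30/15 it understated by 9% (88%); at 15/30 it overstated by 7% (93%). With the placebo rise cut by 40% after Month 5 (slope SD 10/15/25) it overstated by 5/6/8%, where AR(1) understated by 17/21/23%.

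**Trend model.** At equal slope SD 10/15/25, AR(1) understated the slope difference by 11/16/17%, with coverage 95/88/80% (A). B at 20/20: 5.2/31.7 = 16%, with SE 5.6 against a sampling SD of 5.2. Under the placebo bend AR(1) understated by 8/8/6%, while a random intercept and slope fit overstated by 12/15/20% (coverage 92/87/84%).

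**The case against.** Four points carry weight.

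- **The models are supportive.** Neither mean ferritin change nor slope is listed as a primary or secondary endpoint in Protocol 9.1 or SAP 5.2. Under the planned effect the AR(1) tests still rejected in 92–100% of trials. This stands and limits the finding to effect size and interval.
- **The SDs are assumed.** Size and even sign depend on them. In Protocol 1.3 all untreated children in the earlier trial reached 1000 at about 6 months, which points to little spread in slope. This stands. At slope SD 10 the error is still 17% with 77% coverage, but at zero it is 7% with 92%. Unequal spread is possible because the dose rises on a child's own values ("An increasing trend in any of the above 3 measures (SF, LPI, and/or TSAT) at 3 consecutive visits, regardless of value") and only deferiprone is active; which arm spreads more is unknown. Only a placebo bend was simulated, not a bend on deferiprone.
- **The error rate is not shown to improve.** With no true effect and equal slope SD 25, the Month-12 test rejected in 8% of trials under AR(1) and 7.5% under `type=un` (200 trials for the latter, Monte Carlo SE about 1.9 points). These cannot be told apart. The case for `type=un` rests on bias and coverage.
- **The sizes are not for the printed code.** They take baseline as continuous. As typed, `base_sf` acts almost as a fixed intercept per child, so it is not exact to say the printed LS-mean model has no child-level term. That does not rescue it, as the 57% coverage shows.

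**Conclusion.** The CLASS listing is wrong on the face of the code and needs no assumption. The covariance fault is conditional. If children differ in rate of rise, the AR(1) Month-12 difference is biased: about 17–30% understatement at equal slope SD 10–30, about 55% if placebo spread is double, near zero if deferiprone spread is double. Coverage is about 50–77% at equal slope SD 10–25. These figures rest on assumed SDs, straight-line rises, and the difference that would have been seen had withdrawn children stayed on assigned treatment, a target the SAP does not state.

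A reader might infer more than the documents support:

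- *That both models have intervals that are too narrow.* This is mainly a Month-12 LS-mean problem. The trend model's main fault is bias, and its SE was near or above the sampling SD in most cells.
- *That AR(1) should be replaced in the trend model too.* That is a trade-off: the alternative errs by 12–20% in favour of deferiprone if the placebo rise flattens, against 6–8% the other way.
- *That AR(1) is always conservative, or flips at a fixed ratio of spreads.* The sign depends on unknown spreads, and a few simulated cells do not make a rule.
- *That no ferritin is drawn at threshold termination.* The visit list and the schedule disagree. One extra value would not remove the later missingness in any case.
- *That the main result is at risk.* The primary Fisher test and the log-rank tests do not use these models.

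**What to change.** **LS-mean model.**

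1. Remove `base_sf` from CLASS, keep it in MODEL as a continuous covariate, and write `subject=patient(treat)` for `Patient=`.
2. Replace `type=ar(1)` with `type=un`, keeping `ddfm=kr`.
3. Name the non-convergence fallback in advance: `random intercept mon / type=un subject=patient(treat);` in place of the REPEATED line, where `mon` is a continuous copy of month.
4. Report the AR(1) fit as a sensitivity analysis.
5. State that the target is ferritin had withdrawn children stayed on assigned treatment.

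**Trend model.** Keep AR(1), correct `Patient=`, and add a random intercept and slope fit as a sensitivity analysis, noting its direction of error if the placebo rise flattens.

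**Documents.** Reconcile the ferritin entry between the threshold early termination visit (Protocol 5.1) and the End of Study column of the schedule. Carry the code corrections over to LPI and TSAT for consistency; the effect there was not quantified.

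**Cost.** A few SAP lines. Late intervals widen: mean Month-12 SE goes from 44 to 57 at slope SD 15. `type=un` over 12 months has 12 × 13 / 2 = 78 covariance parameters, with on average only 10–19 placebo children giving a Month-12 value, so the fallback must be named. A residual Month-12 error of about 4–9% remains if spread differs by arm. If ferritin is truly AR(1), `type=un` overstates the Month-12 difference by about 7% and the fallback by 14–15%. No gain in null rejection at slope SD 25 can be promised for `type=un`.

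### As the SAP text reads, the Month 8, 11 and 12 contrasts in the Section 5.6 MIXED code have too few coefficients; check the source page and, if it matches, correct them

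*SAP*

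**What the plan says.** SAP 5.6 states that its MIXED code will be used to produce between-group differences, with 95% confidence intervals, in the LS "Mean of change in serum ferritin at Months 1, 2, 3, 4, 5, 6, 7, 8, 9, 10, 11, and 12". The fixed effects are given by "model sf_change = base_sf treat month treat*month", and the CLASS statement begins "class patient base_sf treat month", so baseline ferritin is declared as a class variable.

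Twelve hand-typed ESTIMATE statements follow, one per month. Each has `treat 1 -1` and a treat*month list printed as a deferiprone row and a placebo row. Three of them concern us:

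- The statement labelled "estimate 'Deferiprone - Placebo at Month 8" has the deferiprone row "treat*month 0 0 0 0 0 0 1 0 0 0 0" and the placebo row "0 0 0 0 0 0 0 -1 0 0 0 0/ cl alpha=0.05".
- The statement labelled "estimate 'Deferiprone - Placebo at Month 11" has a deferiprone row of 11 numbers and a placebo row of 12.
- The Month 12 statement has a deferiprone row of 10 numbers and the placebo row "0 0 0 0 0 0 0 0 0 0 -1/ cl alpha=0.05".

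The LSMEANS statement has no DIFF or CL option, so the ESTIMATE statements are the only source of the monthly differences. Table shell 14.2.1.3 has a difference and a 95% CI for every month. The code is offered as the serum ferritin example; the LPI and TSAT shells (14.2.2.3 and 14.2.3.3) have the same layout, and all three have a per-protocol counterpart.

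**The concern.** An ESTIMATE statement assigns coefficients by position. A list that is one number short does not leave a gap where the number is missing: every later coefficient moves one place to the left. A short first row therefore shifts the whole second row into the wrong months, and SAS takes the unfilled places at the end as zero.

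At stake are the baseline-adjusted differences and intervals in Table 14.2.1.3, and those for LPI and TSAT if the block is copied. Two rows could show another month's result under their own label, and the Month 12 row could be empty.

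**Working it through.** **Inputs.** All come from the code in SAP 5.6: two arms, 12 months and the printed coefficient lists. I assume that the analysis data hold month levels 1 to 12 only and that deferiprone sorts before placebo, as the nine complete statements imply. I also assume the usual SAS behaviour of filling from the left and setting missing trailing coefficients to zero.

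**Length needed.** 2 arms × 12 months = 24 places. Places 1–12 are deferiprone Months 1–12 and places 13–24 are placebo Months 1–12. The Month *k* difference needs +1 in place *k* and −1 in place 12 + *k*.

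**Count as printed.**

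| Statement | Deferiprone row | Placebo row | Total | +1 falls on | −1 falls on |
|---|---|---|---|---|---|
| Months 1–7, 9, 10 | 12 | 12 | 24 | place *k* (correct) | place 12 + *k* (correct) |
| Month 8 | 6+1+4 = 11 | 7+1+4 = 12 | 23 | place 7: deferiprone Month 7 | 11+8 = 19; 19−12 = 7: placebo Month 7 |
| Month 11 | 9+1+1 = 11 | 10+1+1 = 12 | 23 | place 10: deferiprone Month 10 | 11+11 = 22; 22−12 = 10: placebo Month 10 |
| Month 12 | 9+1 = 10 | 10+1 = 11 | 21 | place 10: deferiprone Month 10 | 10+11 = 21; 21−12 = 9: placebo Month 9 |

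The SAP says that the code gives 12 monthly differences. As printed, 9 of the 12 are the contrasts that their labels name.

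**What the three contrasts estimate.** Write the mean for arm *a* at month *k* as baseline term + τ_a + μ_k + γ_ak. The true Month *k* difference is τ_D − τ_P + γ_Dk − γ_Pk, because μ_k cancels.

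- Month 8 as printed: τ_D − τ_P + γ_D7 − γ_P7, the Month 7 difference.
- Month 11 as printed: τ_D − τ_P + γ_D10 − γ_P10, the Month 10 difference.
- Month 12 as printed: τ_D − τ_P + γ_D10 − γ_P9. A difference between those two cells would also need μ_10 − μ_9, and the statement has no month coefficients. It is not estimable.

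**Rank check.** I used 64 patients and 12 months, and compared the rank of the model matrix with and without the contrast row.

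| Handling of base_sf | Months 8 and 11 as printed | Month 12 as printed | Months 8, 11 and 12 with 12+12 |
|---|---|---|---|
| Continuous | estimable | not estimable | all estimable |
| CLASS, some values shared across arms | estimable | not estimable | all estimable |
| CLASS, no value shared across arms | not estimable | not estimable | none estimable |

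In the last case Months 1 and 7, which have complete lists, were not estimable either: treatment is then aliased with the baseline levels, so all 12 contrasts fail.

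**How likely is that last case?** The documents do not say to what precision ferritin is reported. Suppose baseline values are spread evenly over the screening range, above 200 and up to 600 µg/L. There are 32 × 32 = 1,024 cross-arm pairs. With whole numbers (400 values) the chance of no shared value is about (399/400)^1024 ≈ 8%. With one decimal (4,000 values) it is about (3999/4000)^1024 ≈ 77%.

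**Extent.** Over SF, LPI and TSAT in the ITT and PP populations there are 12 × 3 × 2 = 72 adjusted differences. Of these, 3 × 3 × 2 = 18 would be affected: 2 × 3 × 2 = 12 repeat another month and 1 × 3 × 2 = 6 are blank.

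**The case against.** The strongest objection is that the defect may lie in the PDF reading and not in the SAP. Every affected row has the right number of zeros after its 1 or −1; only leading zeros are missing, which is what a reader dropping repeated tokens would produce. An author's copy-and-edit slip would give the same pattern. Against loss in reading, equally long runs survive elsewhere: both Month 10 rows keep nine leading zeros and the Month 11 placebo row keeps ten. The documents cannot separate the two explanations. The objection stands, and the point has to depend on a look at the source page.

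A reader might infer that wrong numbers would pass silently into the report. The documents do not support that. The REPEATED statement has `Patient=` where PROC MIXED takes SUBJECT=, so the block cannot run until someone has edited it. After that edit, Months 7 and 8 would be identical adjacent rows, as would Months 10 and 11, and Month 12 would be flagged as non-estimable. A careful output review would probably catch this. SAS would still raise no error for Months 8 and 11.

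A reader might also infer that the primary result at Month 12 is damaged. It is not. The primary endpoint is the percentage of patients with ferritin below 1000 µg/L at Month 12, compared by Fisher's exact test (SAP 5.2.1 and 5.6, Table 14.2.1.5), and it does not use this model. At Month 12 the LSMEANS statement would still give adjusted means by arm, and Table 14.2.1.2 the unadjusted comparison.

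Finally, the intent is plain from the prose, the labels and the shell. That makes the correction easy; it does not make the printed code right.

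**Conclusion.** The point holds, subject to the source check. On the text supplied, three of the twelve ESTIMATE statements are too short. If the source page matches, the code does not deliver the Month 8, 11 and 12 differences that SAP 5.6 assigns to it, and no other line of the block does. What is lost is a supportive result: the adjusted differences and 95% CIs at those months.

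The description of two repeated rows and one empty row rests on SUBJECT= having replaced `Patient=`, and on base_sf being continuous or sharing at least one value across arms. The figure of 18 of 72 is tempting to read as a fixed count. It is an upper figure under those conditions, and it also needs the template to be reused unchanged for LPI and TSAT in both populations. If base_sf stays in CLASS with no shared value, all twelve contrasts fail and mending the coefficient lists alone would not restore them.

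This should be corrected before the code is used. It raises no question about the design or the primary test.

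**What to change.** 1. Check the Month 8, 11 and 12 statements against the source SAP page. If the lists there are complete, only step 3 is needed.
2. Otherwise give each list 12+12 coefficients: Month 8, +1 in place 8 and −1 in place 20; Month 11, places 11 and 23; Month 12, places 12 and 24. Alternatively, drop the ESTIMATE block and use `lsmeans treat*month / diff cl`, keeping the 12 within-month pairs. That needs no typed coefficients.
3. In the same edit write SUBJECT=patient(treat) in the REPEATED statement and remove base_sf from CLASS, so that the contrasts run and are estimable. The `Patient=` option also appears in the trend-analysis block of Section 5.6 and needs the same change.
4. Carry the corrected block to LPI and TSAT.

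The cost is a few lines of SAP code. Design, data collection and trial conduct are untouched.
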